- 5: Patients with CRSwNP/CRSsNP/CRS with and without asthma who have shown low adherence <80% after the cross-sectional study and who have achieved adherence over 80% at follow-up have also developed adrenal function impairment with a reduction in plasma cortisol of at least 8% (exploratory study).

Study design (brief description):

The study design is a cross-sectional study of newly referred patients to the Luftvejsklinik, ENT, RH for investigation and treatment of CRS and possibly asthma. And an exploratory follow-up (pilot project) study of patients who attend 4-month control.

Background:

Chronic rhinosinusitis (CRS) is a condition with chronic inflammation in the nose and sinuses. CRS can be with both nasal polyps (CRSwNP) and without polyps (CRSsNP) (5). 9% of the Danish population is affected by CRS, and about 4% are estimated to be diagnosed with CRSwNP (1). The diagnosis is based on the patient's symptoms and objective signs of inflammation in the nose and sinuses. The symptoms are a blocked nose or nasal secretion, reduced airflow, reduced sense of smell, pain/pressure around the nose, forehead, or eyes. The above symptoms must have been present for more than 12 weeks, and one of the symptoms must be secretion or reduced airflow through the nose to make a diagnosis (6). About 40% of CRS patients in primary care have asthma, whereas 65% referred for treatment at the hospital have asthma (7). CRSwNP that is not satisfactorily controlled particularly affects quality of life (8). It is often characterized by type-2 inflammation, i.e., an increased number of eosinophils in the mucous membranes in the sinuses and nasal polyps - as well as comorbidities such as asthma, ASA/NSAID intolerance (N-ERD), and allergies (5). CRS can be treated both surgically and medically. The basic medical treatment of CRS includes daily saline irrigation and use of nasal steroids. If there is a lot of secretion, antibiotic treatment can also be added to the basic treatment. In the case of nasal polyps, systemic corticosteroid treatment (prednisolone tablets/injection betamethasone) can also be added (5,6). If the medical treatment is not

optimal, patients can be offered surgical treatment - endoscopic sinus surgery (ESS) (5). The goal is to aim for the removal of polyps in the nose and sinuses.

Comorbidity:

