The use of steroids is a part of medical treatment for CRSwNP and asthma, and systemic steroid use is often seen in moderate to severe cases. It can affect the body's own production of hormones, which at different doses can trigger adrenal insufficiency. The condition is divided into primary and secondary adrenal insufficiency (22). Primary adrenal insufficiency involves the body's reduced or complete lack of hormone-producing cells in the adrenal cortex. Secondary adrenal insufficiency is caused by reduced production or effect of ACTH from the pituitary gland in the brain (2, 22, 23). The most common form of secondary adrenal insufficiency develops during external steroid treatment with pharmacological doses for a non-endocrine disease, such as CRSwNP and asthma. About 25% of patients receiving long-term steroid treatment develop long-term adrenal insufficiency - the higher the dose and treatment duration, the greater the risk (2, 23). Adrenal insufficiency can also occur with locally administered steroids - for example, it has been shown that 8% of patients treated with inhaled steroids, 52% after intramuscular injection, and more than a third of patients in long-term low-dose steroid treatment develop insufficiency (23, 24). In addition, steroid creams have been shown to have systemic side effects in a previously unknown high number of patients (3). Reduced production of steroids from the adrenals is a situation that should be considered in connection with acute illness, but also surgery (22, 25). Many patients with CRSwNP are offered 1-3 injections of steroids annually, in addition to high doses of nCS. Surgical intervention is also performed in between these injections. Here, one could consider supplementing preoperatively with steroids as protection against the stress of surgery if the endocrine axis is affected. Systemic glucocorticoids are used as treatment for a wide range of diseases, such as inflammatory diseases like CRSwNP or asthma either as needed or chronically (26-28). Glucocorticoid-induced osteoporosis is the most common secondary cause of osteoporosis and is a global public health problem, where fractures contribute to significant morbidity and mortality (29). The frequency of secondary glucocorticoid-induced osteoporosis is unknown in patients with CRSwNP (26). Prevention of this and negative consequences should be a focus point for healthcare professionals in these patients due to long-term treatment with systemic glucocorticoids (28).

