Patients for the project are recruited at the initial visit to the [Luftvejsklinik](#). A nurse from the clinic will inform about the project and ask if the patient is interested in participating. If the patient is interested, a meeting will be arranged with a researcher from the research group (see section on information).

Inclusion/exclusion criteria for the cross-sectional study:

Inclusion criteria:

- Diagnosed with CRS and possibly asthma
- Age over 18 years

Exclusion criteria:

- Do not read or speak Danish
- Severe psychiatric comorbidities

Patients who have never taken systemic steroids

- According to investigators' experience, cannot participate or comply with local treatment.
- Do not give permission to access FMK-online

Inclusion/exclusion criteria for exploratory study - 4 months follow-up (pilot project):

Inclusion criteria:

- Diagnosed with CRS and possibly asthma
- Age over 18 years
- Low adherence: Foster score, i.e. number of treatments taken compared to prescribed <80% (4 weeks out of 16 weeks) and/or measured on MARS-5 L/N ≤ 35 at first visit (equivalent to less than 80%). If the patient does not have asthma, it is MARS-5N ≤ 19 .
- If asthma: ACQ ≥ 1.2 or ACT ≤ 17 (partially uncontrolled asthma)
- SNOT-22 score ≥ 35 (partially uncontrolled CRS)
- Participation in cross-sectional study at initial visit to Respiratory Clinic

Exclusion criteria:

- Adherence: Foster score > 80% and/or on MARS-5-L/N > 35 points at first visit
- Cannot read or speak Danish
- Severe psychiatric comorbidities
- Patients who have never taken systemic steroids
- According to investigators' experience, cannot participate or comply with local treatment
- Do not give permission to access FMK-online

Method of investigation:

Demographic information:

Height, age, gender, weight, lung function.

Blood tests:

Leukocytes and differential count, allergy blood tests with a package of specific allergens (routine). Research blood test plasma cortisol.

Synacthen test:

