Statistical analysis of the data will be performed using IBM SPSS Statistics. Results will be presented as mean, SD, median, range, and 95% CI. Parametric data will be compared using paired tests, and non-parametric data using Mann-Whitney Test. Categorical variables will be tested using the chi-square test.

Power calculation for cross-sectional study and exploratory follow-up at 4 months (pilot project):

Rationale: In a recent study on severe asthma, patients received daily tablet prednisolone (>5 mg) for 3 months. 60% of the patients had adrenal insufficiency, 33% had total insufficiency, and 27% had partial insufficiency (32). Patients with CRS are often treated with steroid injections in Denmark, receiving an average of three steroid injections per year (clinical observation, REDCap, Global airways incl. biological treatment). Some receive up to six injections per year, with an effect lasting approximately 6-8 weeks per injection. This means that patients with CRS are only covered for about 6 months out of 12 months per year. This is different from severe asthma with daily treatment. Therefore, we estimate that we can detect half of the findings from the asthma study (32). We therefore expect that half of the 60% who develop insufficiency in the asthma study = 30% of the CRS patients will have adrenal insufficiency. As some will have received steroid injections several months ago, a slight reduction is estimated to 25%. But no less than 25%, as many receive high-dose nasal steroids, which, like steroid cream, may cause adrenal insufficiency (3). The 25% is our best estimate. It may be higher but not lower. The literature has documented that 8% of a population have adrenal insufficiency without having received supplemental steroids before the test. To

demonstrate a difference between the background population and our population with 25% adrenal insufficiency, we will need to investigate 72 patients with an alpha value of $p < 0.05$ and a power of 80%, and with a dropout rate of 10%, we will need to test around 80 patients (cross-sectional study).

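### The protocol's 72 patients for 80% power fits a two-group comparison, but one group is enrolled and compared with an uncited 8%; power against a fixed 8% is about 97–98%

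*Protocol*

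**What the plan says.** The section on the power calculation (Protocol, after Statistical analysis) contains the only sample-size justification. It halves a 60% rate from a severe-asthma study to 30%, then reduces that to 25% because some injections will have been given months earlier. On this figure it says "The 25% is our best estimate. It may be higher but not lower". The comparator is described thus: "The literature has documented that 8% of a population have adrenal insufficiency without having received supplemental steroids before the test". No reference, sample size or interval accompanies it. To "demonstrate a difference between the background population and our population with 25% adrenal insufficiency, we will need to investigate 72 patients" at alpha 0.05 and 80% power, rising to about 80 for 10% dropout. Neither a formula, nor sidedness, nor a number of groups is given.

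Elsewhere:

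- Study design: "The study design is a cross-sectional study of newly referred patients to the Luftvejsklinik, ENT, RH". No background cohort is described.
- The exclusion criteria for the cross-sectional study include "Patients who have never taken systemic steroids", so no enrolled subgroup can supply the background rate.
- Statistical analysis: "Categorical variables will be tested using the chi-square test".
- The background section on glucocorticoid-induced adrenal insufficiency gives another 8%, with references: "it has been shown that 8% of patients treated with inhaled steroids, 52% after intramuscular injection".
- Primary outcome: whether prolonged systemic steroid use has affected the patients' own cortisol production, specified as baseline plasma cortisol under 500 nmol together with a correlation with lifelong steroid use. Secondary outcome 1 concerns stimulated cortisol not exceeding 500 nmol.

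**The concern.** A comparison of two sampled groups and a comparison of one group with a known rate need very different numbers, because the second carries no sampling error in the reference. The stated 72 looks like the first, while the design looks like the second. If so, the 80% does not describe a one-group comparison, and the reader cannot see how much the result depends on the 8%.

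That dependence matters for the conclusion. A finding that patients exceed the background is only as sound as the background figure, which has no source. The paragraph also treats 25% as a lower limit, which rules out by assertion the true rates at which power would be low. Finally, the calculation concerns the prevalence of a condition that it does not define, and it is not tied to any listed outcome.

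**Working it through.** **Inputs.** Reference p0 = 0.08, patients p1 = 0.25, alpha 0.05, power 80%, n = 72 and dropout 10%, all from the power-calculation section. Two-sided testing is assumed, as sidedness is not stated. The normal quantiles are 1.960 and 0.842; the difference is 0.17.

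**1. Reproducing the 72 as a two-group size (per group).**
- Pooled variance: [1.960·√(2·0.165·0.835) + 0.842·√(0.08·0.92 + 0.25·0.75)]² / 0.17² = 73.6, so 74.
- Unpooled variance: (1.960 + 0.842)²·(0.0736 + 0.1875) / 0.0289 = 70.9, so 71.
- Full enumeration of the uncorrected chi-square test, 72 against 72: power 80.9%.
- Dropout: 72/0.9 = 80, as stated.

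So 72 fits a two-group calculation. This origin is inferred.

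**2. One group against a fixed 8%.**
- Normal formula: [1.960·√(0.08·0.92) + 0.842·√(0.25·0.75)]² / 0.17² = 27.8, so 28.
- Equal-tailed exact binomial test: 80% is first reached at n = 35 and holds from n = 40.
- The largest version tried, using the variance at 25% only, gives 50.9.

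None is near 72.

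**3. Power of 72 patients against a fixed 8%.** With X ~ Binomial(72, p), the equal-tailed exact test rejects high at X ≥ 12 (upper-tail probability at 8%: 0.0115). The one-sample chi-square test rejects high at X ≥ 11 (0.0275), since (11/72 − 0.08)/√(0.08·0.92/72) = 2.28 exceeds 1.96.

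| True rate | Exact, ≥12 | Chi-square, ≥11 |
|---|---|---|
| 25% | 97% | 98% |
| 20% | 80% | 88% |
| 18% | 66% | 77% |
| 15% | 40% | 52% |

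The word exact does not fix the test by itself. An exact test that orders outcomes by likelihood gives p = 0.0455 at 11/72, so it also rejects from 11.

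**4. A different fixed reference (assumed values), test reset to it, true rate 25%.**

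| Reference | Exact (cut-off) | Chi-square (cut-off) |
|---|---|---|
| 10% | 89% (14) | 94% (13) |
| 12% | 83% (15) | 83% (15) |
| 15% | 55% (18) | 65% (17) |

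**5. False positives if 8% is too low.** Suppose patients and the correct reference are both at 12% (assumed), with the test still against 8%. It rejects with probability P(X ≥ 12) = 15% (exact) or P(X ≥ 11) = 24% (chi-square), against a nominal upper tail of 2.5%.

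**6. If the 8% is an estimate from a published sample of m people (assumed).** Enumerated two-sample chi-square power, 72 at 25% against m at 8%: 69% for m = 50, 81% for 72, 89% for 100 and 94% for 200.

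**The case against.** The best defence is that nothing was miscalculated. The text speaks of a difference between two populations and the protocol names the chi-square test, so a two-sample comparison with a published sample may be meant. Then 72 is right, provided that sample has about 70 people or more. This reading is legitimate, but it requires the sample and its size to be named, and neither is. What stands is that the 80% cannot be attached to an identifiable comparison.

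It is also fair that the error is conservative on the protocol's own rates. A reader might infer that the surplus disappears unless 8% is exactly right. For power that is too strict: step 4 shows at least 83% up to a reference of 12%, and step 6 at least 81% for a source of 72 or more. It is false-positive control that depends on the 8%. Nor should a reader conclude that real power is 55%: that figure needs a 15% reference, which no section gives as a background rate, and the chi-square test gives 65%.

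The two 8% figures might be read as a contradiction or as leaving the comparator unknown. They do neither. The power section says whom its 8% describes, people without supplemental steroids; the other concerns inhaled-steroid users. Only the source is missing.

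On the 25%, the protocol offers more than the analogy with steroid cream: its background section cites about 25% with long-term treatment, 52% after intramuscular injection and more than a third on long-term low doses. These make 25% plausible but do not make it a minimum.

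Finally, one might infer that the calculation serves no part of the primary outcome. The documents do not settle that: the outcome opens with an effect on the patients' own cortisol production, which is close to adrenal insufficiency, and the calculation leaves that term undefined.

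**Conclusion.** The point holds as a fault in the stated justification and should be fixed; it does not show that the study is too small. For the single group described, 72 evaluable patients have 97% (equal-tailed exact) or 98% (chi-square) power at 25% against a fixed 8%, not 80%. The two-group origin of 72 is an inference, but this conclusion does not need it: it rests on two-sided 5% testing, 8% treated as known and a true 25%.

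Power falls below 80% for true rates under about 20% (exact) or 18.5% (chi-square), cases that the paragraph excludes without sufficient grounds. A claim of excess over the background needs a sourced reference rate, as the 15% to 24% rejection probability at an assumed common rate of 12% shows.

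**What to change.** Keep 80 enrolled and rewrite the paragraph.

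- **Comparison.** Restate it as a one-sample comparison with a fully named test, for example: *Treating 8% [source] as known, 72 evaluable patients give 98% power at a true 25%, 88% at 20% and 52% at 15% (one-sample chi-square test, reject at 11 or more of 72).* For the equal-tailed exact binomial test (reject at 12 or more) the figures are 97%, 80% and 40%. Alternatively, keep the two-sample calculation, name the published reference sample and its size, and give the power for that size.
- **Reference.** Cite the source of the 8%.
- **Assumed rate.** Present 25% as an assumption and delete the statement that it cannot be lower.
- **Endpoint.** Define adrenal insufficiency for this calculation and state which listed outcome it powers. It is a prevalence, whereas the primary outcome is specified as a baseline cortisol level and a correlation with lifelong steroid use.

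The cost is one paragraph and one citation. Enrolment and procedures do not change. The trade-off is that the text will show openly the lower power at true rates below 20%.

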Protocol - Adherence in Global Airways – the relationship between steroid intake and the impact on the endocrine axis, bone density, and structure in patients with chronic sinusitis and asthma

Research Group:

Clinical Nurse Specialist, Cand. Cur, [name] (PI)

Clinical Nurse Specialist, Cand. Cur, [name]

Chief physician and Ph.D., Ear-Nose-Throat, [name]

Professor and Chief physician, Endocrinology, [name]

Professor and Chief physician, Pulmonology, [name]

Introduction:

There has been a significant focus on ensuring treatment of diseases in both upper and lower airways (global airways) simultaneously because they have the same inflammatory disease mechanism.

Approximately 9% have chronic sinusitis (CRS), 4% of the Danish population is diagnosed with CRS with nasal polyps (CRSwNP)(1), and 7-10% have asthma. Over the years, some of these patients have been treated with systemic and/or locally acting steroids (glucocorticoids). These patients referred have moderate to severe disease with a significant disease burden, and therefore continue to be treated with steroids. The risk of developing secondary adrenal insufficiency is high with prolonged use of systemic high-dose and potent glucocorticoids but can also occur with locally administered glucocorticoids (2). It has recently been demonstrated that treatment of eczema with steroid-containing creams has indications of side effects not only on the skin but also on the bones (3). Moreover, there is an additive effect, so that it is the total burden of steroid intake that is significant for the development of side effects, but whether it also affects cortisol response to ACTH is unknown (4). Treatment with steroids currently affects the endocrine axis (P-cortisol), increasing the risk of osteopenia, osteoporosis, and possibly diabetes. Our knowledge of which preparations, doses, and modes of administration cause these side effects is inadequate, and whether the total dose over time is significant is unknown. This gives rise to conducting a cross-sectional study to determine the significance of these side effects, followed by an exploratory follow-up study of patients with global airway diseases and high adherence (80%) to local treatment.

Purpose:

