The purpose is to investigate the relationship between high total intake of systemic steroids in patients with upper and lower airway disease, low endogenous cortisol production, and reduced bone density and structure. Additionally, through an exploratory follow-up (pilot project) study, to investigate whether improved adherence to local steroid treatment and biologic medication would decrease the patient's endogenous cortisol production.

Hypothesis/research question:

Patients with CRS/CRSnNP/CRSwNP who have received systemic steroids have an impact on the adrenals with low basal P-cortisol (below 500nmol), abnormal response to stimulation with ACTH (synacthen test) measured at the final P-cortisol. Additionally, a reduced increase (delta value) in P-cortisol is expected in connection with a synacthen test. These patients also have an affected bone density and structure with a higher incidence of osteopenia and osteoporosis than expected for this age group. Patients with CRS/CRSnNP/CRSwNP who can improve their adherence to >80% have an increasing impact on P-cortisol.

Primary outcome:

The primary outcome is to investigate whether newly referred patients with upper and possible lower respiratory tract diseases have an impact on their own cortisol production after prolonged use of systemic steroids. That is, the baseline level of plasma cortisol is <500 nmol, and a correlation with lifelong use of systemic steroids can be demonstrated.

Secondary outcomes:***Cross-sectional study:***

- 1: After a stimulation test, plasma cortisol is not above 500 nmol.
- 2: The increase in plasma cortisol is associated with the intake of systemic steroids.
- 3: Demonstration of the correlation between lifelong use of systemic steroids and the degree of osteopenia and osteoporosis (T-score). T-score from DEXA scanning is used to measure bone density and structure. An affected T-score is defined as follows: T-score between -1.0 and -2.5 = osteopenia and score \leq -2.5 = osteoporosis.
- 4: The number of patients with osteoporosis/penia of the spine and femur is increased compared to expected findings in age-matched individuals.

Exploratory follow-up at 4 months (pilot project):

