
Method:

Regarding 1) In the cross-sectional study, patients will receive the standard investigation and treatment at the Luftvejsklinik. This includes investigation for airway disease and possible type-2 inflammation,

treatment, etc. Measurement of their adherence and possible optimization of CRS and asthma treatment. The total amount of systemic steroids will be calculated and included in the study.

Experimental intervention (synacthen test): To investigate how prolonged use of systemic steroids and adherence affect cortisol production, all patients who agree to participate in the project will undergo a synacthen test. A synacthen test is used to assess whether the body's adrenal glands produce cortisol satisfactorily (i.e., own production). Cortisol is a hormone produced in the adrenal glands and is therefore called adrenal cortex hormone. It has a few effects, including on muscles, supportive tissues and bones, and nutrient metabolism. Therefore, the adrenal glands' ability to produce hormones is important. Reduced or absent production of adrenal cortex hormones can be seen with prolonged treatment with systemic steroids (adrenal cortex hormones). A synacthen test will be performed twice in total on all patients. The first time is at the 1st visit (preliminary examination) and the second time at the 4-month follow-up.

Ad 2) Exploratory investigation/4-month follow-up (pilot project): The experimental intervention in the follow-up involves measuring P-cortisol in patients who have now achieved high adherence (> 80%). Patients will receive standard follow-up/monitoring and treatment in the respiratory clinic.

Study population:

The study population consists of patients referred to the Luftvejsklinik, ENT, RH, for evaluation of CRS/CRSwNP/CRSnNP and with or without asthma for biological treatment. They are classified according to the type of inflammation they have (type-2 or non-type-2), whether they have CRSwNP or CRSsNP, their adherence, comorbidity with asthma, and finally the severity of the disease. All patients are given standard questionnaires to assess CRS/CRSwNP/CRSnNP and asthma (STARR-15, SNOT22, ACQ, ACT, MARS-5-L/N, Fosterscore - routine questionnaires for all patients in the Luftvejsklinik).

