In the exploratory follow-up at 4 months (pilot project), we will investigate whether good adherence (>80%) to nasal steroids versus continued poor adherence (<80%) changes in P-cortisol compared to measurement of P-cortisol from the cross-sectional study. It is not known whether good adherence (>80%) changes adrenal function. This pilot project will be used for a possible future study, where the effect of adherence will be the primary focus. Therefore, we will include all 80 patients from the cross-sectional study and divide their results into good and poor adherence.

Extraction of biological material:

A maximum of 14 ml of blood is extracted during each Synacthen test (minimum 0.5-3.5 ml maximum split tube x 2-, and 3.5-ml maximum x 2 for the first blood sample for P-cortisol baseline and for the second blood sample for P-cortisol determination). The first blood sample is collected for P-cortisol measurement before the IV injection of ACTH and a minimum of 0.5 ml and a maximum of 3.5 ml of blood is extracted. The second blood sample is collected after 30 minutes following the IV injection of ACTH, and a minimum of 0.5 ml and a maximum of 3.5 ml of blood is extracted. The material is destroyed after analysis. Therefore, no research biobank will be established.

Information from patient records:

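### Exploratory four-month follow-up: the protocol contradicts itself on who is followed and retested, gives two different adherence splits, and sets adherence entry criteria that are not complements

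*Protocol*

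**What the plan says.** **Who is followed.**
- The criteria for the exploratory study (Protocol Summary, repeated in the protocol body) require low first-visit adherence: Foster below 80% and/or MARS-5 L/N at most 35, or MARS-5N at most 19 without asthma. They also require SNOT-22 of at least 35 and, with asthma, ACQ of at least 1.2 or ACT of at most 17. One exclusion reads "Adherence: Foster score > 80% and/or on MARS-5-L/N > 35 points at first visit".
- Method, on the Synacthen test: "A synacthen test will be performed twice in total on all patients", the second time at four months. The same section later describes the follow-up as "measuring P-cortisol in patients who have now achieved high adherence (> 80" per cent).
- The power calculation section: "we will include all 80 patients from the cross-sectional study and divide their results into good and poor adherence".
- Study design: the follow-up covers patients who come to the four-month check-up, with no further limit.
- Introduction: "exploratory follow-up study of patients with global airway diseases and high adherence (80%) to local treatment".

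**Who is compared.**
- The follow-up paragraph of the power section opens with "good adherence (>80%) to nasal steroids versus continued poor adherence (<80" per cent) and closes with the division of all 80 quoted above.
- The hypothesis concerns patients "who can improve their adherence to >80% have an increasing impact on P-cortisol".
- Secondary outcome 5 concerns those "who have shown low adherence <80% after the cross-sectional study and who have achieved adherence over 80% at follow-up".

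**The concern.** A first-visit high adherer is barred from the follow-up by one section and retested at four months by two others. Clinic staff cannot tell from the protocol who has the second ACTH test, and the analyst cannot tell who belongs in the data set.

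The grouping has a related fault. The question is about change from low to high adherence. A good/poor division of everyone includes patients whose adherence was high from the start. Any cortisol difference between such groups would partly reflect people in whom nothing about adherence improved.

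Outcome 5 is a listed secondary outcome, and the protocol says the pilot will be used for a possible later study with adherence as its main focus. A pilot with an unclear population and contrast is a weak basis for that study.

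**Working it through.** **1. Where the 80 comes from.** The power section gives 8% versus 25%, alpha 0.05, power 80%, 72 patients and 10% dropout. The unpooled two-proportion formula, two-sided, gives (1.960 + 0.842)² × (0.08 × 0.92 + 0.25 × 0.75) / 0.17² = 70.9, so 71 per group; the pooled version gives 74. The stated 72 lies between them. Then 72 / 0.9 = 80. So 80 is a recruitment figure that already contains the dropout allowance, and the protocol's own evaluable number is 72. The follow-up has no sample size of its own.

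**2. Can the population statements all hold?** The cross-sectional criteria are a CRS diagnosis with possible asthma, age, language, psychiatric comorbidity, prior systemic steroid use, ability to follow local treatment, and access to medication records. None limits adherence or symptom scores. The 80 can therefore include first-visit high adherers and patients outside the SNOT-22 or ACQ/ACT limits. The follow-up criteria leave them out; the Method and power sections retest and analyse them.

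**3. Size of the gap.** The protocol gives no adherence rate for this clinic. Its Adherence section cites 22% to 78% for asthma and COPD. Borrowing that range, as an assumption, for the share L with low first-visit adherence:

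| L | 80 × L | 72 × L |
|---|---|---|
| 22% | 17.6 | 15.8 |
| 50% | 40 | 36 |
| 78% | 62.4 | 56.2 |

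About 18 to 62 of 80 pass the adherence criterion, and the SNOT-22 and ACQ/ACT limits can only lower this. Those limits also remove some low adherers who might improve, so the number of improvers may differ between the two readings.

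**4. What a split of all 80 does.** Take L = 50% and suppose half of the low adherers improve (both assumed). That gives 20 low-to-high, 20 low-to-low and 40 adherent at the first visit. Classified at follow-up, with the 40 still adherent, the good group is 20 + 40 = 60, and 40 of those 60 did not change. Any of the 40 who lapse join the poor group, although their adherence was not continuously poor. Classified at the first visit instead, the 20 improvers and the 20 non-improvers share one group. The closing sentence does not say which visit applies, and neither version yields improved versus continued poor. Across L = 22% to 78% and an assumed 25% to 75% improving, the low-to-high group is about 4 (80 × 0.22 × 0.25) to 47 (80 × 0.78 × 0.75).

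**5. The adherence criteria, for patients assessed on L/N.**

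| Foster | MARS-5 L/N | and/or read as OR | read as AND |
|---|---|---|---|
| 70% | 35 | inclusion only | inclusion only |
| 70% | 36 | both | neither |
| 90% | 35 | both | neither |
| 90% | 36 | exclusion only | exclusion only |

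Two of the four combinations are unresolved on either reading. These are combinations, not patients; the protocol gives no rate of disagreement between the instruments.

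Foster of exactly 80% is in neither limit. It cannot arise from days out of seven (5/7 = 71.4%, 6/7 = 85.7%), but it can arise from treatments taken over treatments prescribed, which is how the criterion describes the score.

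The inclusion cut of MARS-5N at most 19 has no counterpart in the exclusion.

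**The case against.** **There are not several rival populations.** This largely stands for two of the statements. The Method wording about patients who have now reached high adherence, and outcome 5, can be read as the low-to-high subgroup of those admitted by the follow-up criteria. A reader might infer that these exclude a continued-poor group altogether. They do not, because the same Method section retests everyone and the power section names that comparator. The Introduction's wording does conflict with a low-adherence entry criterion, and the clash between the criteria and the Method and power sections remains.

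**The criteria have a workable outcome.** If any exclusion bars entry, patients on L/N enter only when low on both instruments. That is a fair default, but it empties the inclusion's or of meaning for them.

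**Patients without asthma.** A reader might infer that a low Foster score with a high MARS score excludes patients with asthma but not those without. The protocol does not support this firmly: it gives no MARS score range, and the MARS-5N cut may be meant to carry over to the exclusion. What can be said is that its application without asthma is unclear.

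**Grouping can be left to the analysis plan.** The detail could be. But the protocol itself states two different splits, and only the first fits outcome 5.

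**It is an unpowered pilot.** True, and this limits the importance of the point. It does not settle who is retested.

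**Conclusion.** The contradiction is real and should be fixed; confidence is high. It is confined to the exploratory follow-up and outcome 5. A reader might carry it over to the primary outcome or the sample size, but neither depends on who is followed up.

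On one reading the follow-up holds at most 80 patients, about 72 after dropout. On the other it holds fewer, and how many fewer rests on an adherence range borrowed from asthma and COPD. The protocol does not support a count for this clinic, a claim that the number of improvers is the same on both readings, or an estimate of the effect on the cortisol difference.

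**What to change.** Reconcile the Introduction, Study design, Method, both copies of the follow-up criteria, and the power section on who is followed and who has the second test. State one adherence rule: which instrument decides when the two disagree, how exactly 80% is classed, and which MARS cut applies with and without asthma. Make the exclusion the exact complement of the inclusion, or delete it.

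- **If all 80 are followed:** remove the adherence, SNOT-22 and ACQ/ACT limits as follow-up entry criteria. Derive one three-level variable: low-to-high, low-to-low, high at baseline. Use low-to-high for outcome 5 and low-to-high versus low-to-low for the power section's comparison, and report baseline adherers separately. No tests are needed beyond those the Method section already plans.
- **If only low adherers are followed:** correct the statements that all patients are tested twice and that all 80 are included, and make clear that patients whose adherence stays poor are also retested.

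The cost is protocol wording and, on the first option, one derived variable. The comparison groups are smaller than under a split of all 80, so intervals are likely to be wider.
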